#### 5.4 Taking test sensitivity, specificity and cross-reactivity into account

PCR tests can be regarded as effectively 100% specific, but they have a short detection window, which varies between individuals. We refer to this as the test's persistence distribution. Serological tests vary in their specificity and sensitivity. Failures of specificity (false positives) can arise for several reasons. While some may be due to a random signal that has exceeded the test's threshold, other false positives may be due to cross-reaction to antibodies to related viruses. Currently available DENV and ZIKV IgM tests react to each other's IgM, and to other flavivirus IgM. We can therefore anticipate that ZIKV and DENV IgM test specificity might vary between collaborating centers, reflecting the geographical distribution of other viruses to which they are cross-reactive. In addition, although IgM antibody is usually assumed to persist for 12 weeks, in some individuals it may persist for many months. Therefore, if IgM is due to an infection acquired many months before the pregnancy, we might regard it as an *analytic* true positive, but a *diagnostic* false positive.

Information on the effective sensitivity and specificity of IgG and IgM assays in different centers is currently incomplete, but will be systematically developed under the ZIKA-VID program. Sources of data on properties of diagnostic tests, for use in ZIKA-VT data analyses, will be updated regularly (see *Appendices 3 & 4*).

Reliable estimates of the sensitivity and specificity of each individual test are not, by themselves, enough to determine the probability that a woman has experienced an infection in pregnancy given her test results. Each woman will be tested on multiple occasions, and on multiple tests. Interpretation of these sequences of tests is complex as we can anticipate there are strong correlations, conditional on true infection status, both between tests results at the same time, and between tests of the same type over time. Rules for determining whether a sequence of tests and clinical findings should be considered as a reflecting a "confirmed", "definite" or "possible" maternal infection will be drawn up by the Expert Diagnostics Group (*Appendix 1*).

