#### 7.4 Analysis of gestational age at maternal infection

We start with an analysis that assumes perfect test sensitivity and specificity. The gestational age at the onset of maternal infection is  $\pi_i(t)$ , t in weeks. Although the period of interest is between just before conception and delivery, ie the interval  $-2 \le t \le G_i$ ,  $\pi_i(t)$  is defined over a wider interval  $-2 - D \le t \le G_i + D$ , where D is the maximum duration of a test of persistence. This is because a first IgM+ test D weeks after delivery, or an IgM- test D+2 weeks before conception, both provide information about the probability of infection during pregnancy. Because there may be a finite probability that the maternal infection occurred before conception,  $\sum_{-2 \le t \le G_i} \pi_i(t)$  can take any value

between 0 and 1. Some special cases help clarify the concepts:

7.4.1 Onset of infection marked by symptoms. If a woman has symptoms in pregnancy starting at T then  $\pi_i(t) = 1$ , if t = T and  $\pi_i(t) = 0$ , if  $t \neq T$ .

7.4.2 Seroconversion alone. If the interval is defined by seroconversion during pregnancy, ie between a last lgG- at  $t_1$  and a first lgG+ at  $t_2$ , then in the absence of any other information,

$$\pi_i(t) = 1/(t_2 - t_1 + 1)$$
, if  $t_1 \le t \le t_2$ , else 0.

7.4.3 Surveillance data alone. Alternatively, suppose there are surveillance counts M(t) of suspected or confirmed cases (of ZIKV, DENV, or CHIKV) depending on the disease being studied [4], then the "a priori" distribution of when the infection might have occurred (given that it occurred in pregnancy) can be represented as a Dirichlet distribution:

$$\pi_i(t) = \alpha(t), \quad \alpha(t) \sim Dirichlet(M(t)), \quad -2 \le t \le G_i$$

7.4.4 PCR+ or IgM+, no surveillance data. If the specified interval is defined by a PCR+ or IgM+ test at time  $t_2$  and the earliest possible date of infection was  $t_1$  (which might be marked by an IgM- result, or  $t_1 = t_2 - D$ ) then, if the cumulative persistence distribution (the probability that persistence is d or less weeks) is  $F(d,\theta)$  with parameter(s)  $\theta$ , then (dropping the  $\theta$ ):

Author: [name] (UNIVBRIS)

20

$$\pi_i(t) = \frac{F(t_2 - t)}{\sum_{t_1 \le u \le t_2} F(u - t)}, \text{ if } -2 \le t \le t_2, \text{ else } 0$$

7.4.5 PCR+ or IgM+ with surveillance data. Now we assume the same test results, but surveillance data is available as well:

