#### 8.2 Analyses of properties of diagnostic tests

As noted earlier the ZIKA-VT and ZIKA-VID programs are inter-related and the analyses set out in *Section 7.5* will provide the definitive information on the persistence of IgM and other tests.

However, the population epidemiology data collected by ZIKA-VT also provides an opportunity for *supportive* analyses of test persistence, sensitivity and specificity. Results should be compared with the more formal evaluations undertaken as part of ZIKA-VID, which will comprise evidence from published literature as well as findings from *de novo* field work.

8.2.1 Average persistence of IgM. Given estimates of IgM prevalence (section 8.1.5) and incidence of primary infections based on seroconversion (section 8.1.4) or changes in cumulative incidence (section 8.1.6), estimates of the average persistence of IgM can be estimated by dividing IgM prevalence by IgM incidence.

We anticipate that IgM persistence may differ in women with previous ZIKV or DENV infections. If these women can be identified by avidity tests it will be possible to generate separate estimates of average IgM persistence for primary and secondary infections

8.2.2 Sensitivity and cross-reactivity of IgM and IgG tests. Estimates of sensitivity will be available for IgM and IgG tests in women with infections confirmed by PCR, and from cases where tests failed to detect infections in mothers of babies in whom congenital infection is demonstrated.

8.2.3 Specificity of IgM and IgG tests. Specificity of IgG tests can only be estimated in populations which are known to have not been exposed to the infection in question: this means that data collected in ZIKA-VT is not relevant to estimates of IgG specificity. However, IgM specificity can be studied by observing the relationship between the proportion of tests which are positive and the surveillance data over the previous 12 months. IgM persistence is believed to be about 12 weeks on average, so that an IgM+ occurring at a time when surveillance sources indicate there has been no virus circulating for over 4 or 5 months are highly likely to be false positives from a diagnostic point of view, whether due to persistent antibody, cross-reactions, or other factors; although it will be important to be able to rule out foreign travel before making these inferences. Data of this sort will be of great importance in defining the tails of the persistence distributions of IgM tests

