## Table 2. Listing of all congenital anomalies at delivery

#### Including:

Most likely trimester of maternal infection
Ultrasound findings
Outcome of pregnancy: fetal death, stillbirth, livebirth
Gestational age at delivery (GA)
Birthweight, birthweight for GA, head circumference, head circumference for GA.
Description of anomalies at delivery: cranial morphology; brain anomalies; congenital contractures; neurological sequelae.

Author: [name] (UNIVBRIS)

Table 3. Outcomes of pregnancy: generic summary tables and covariate analyses

- Individed	- .	1		T					
	Trimester	Symptoms	Number of						
	of	during	Mothers in						
	presumed	pregnancy	category						
	infection	,,							
	1	Yes							
Monthoul		No		Outcomes of pregnancy to be					
Vertical	2	Yes		tabulated.					
infection		No		-					
ZIKV	3	Yes							
		No		Abnormal ultrasound findings					
	1	Yes		Abnormal ultrasound findings:					
Vertical		No		specific abnormalities, groups of					
Infection	2	Yes		abnormalities, etc. to be tabulated					
DENV		No		Fetal deaths (1 st and 2 nd trimester)					
	3	Yes		Fetal deaths (3 rd trimester)					
		No		Livebirths					
	1	Yes							
		No		Covariates to be considered for					
Vertical	2	Yes		regression analysis Centre					
Infection		No							
CHIKV	3	Yes		Year - season					
		No		Co-infections in the mother					
Maternal	1	Yes							
infection		No		Previous infection in mother, same or					
NO vertical	2	Yes		different arbovirus					
infection		No		Maternal age					
ZIKV	3	Yes		Obstetric history (e.g. previous stillbirth,					
		No		congenital abnormalities)					
Maternal	1	Yes		Comorbidities (e.g. sickle cell, diabetes)					
infection	_	No		Smoking /alcohol /drug use					
NO vertical	2	Yes		SES markers					
infection	_	No							
DENV	3	Yes							
	3	No							
Maternal	1	Yes							
infection	_	163							
NO vertical		No		1					
infection		140							
CHIKV	2	Yes		1					
J	_	No		1					
	3	Yes		1					
	3			1					
		No	1						

Author: [name] (UNIVBRIS)

Table 4. Outcomes by birth cohort: generic summary tables and covariate analyses

	Trimester of	Symptoms during	Number of Mothers	Outcome	Outcomes to be tabulated:
	presumed infection	pregnancy	in category		Number (%) preterm <37 completed weeks
	1	Yes			Gestational age (mean, sd)
		No			Number (%) livebirths
Vertical	2	Yes			Number (%) neonatal deaths
infection		No			Number (%) deaths at one year
ZIKV	3	Yes			Birthweight (mean, sd)

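### Section 8.2.3 reads IgM+ results after 4 or 5 virus-free months as likely false positives without regard to gestational age, so late-pregnancy tests can count true early-pregnancy infections against specificity

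*SAP*

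**What the plan says.** Section 8.2.3 proposes to study IgM specificity by relating the proportion of positive tests to surveillance over the preceding 12 months. It starts from the statement that "IgM persistence is believed to be about 12 weeks on average". It then says that IgM+ results arising when "surveillance sources indicate there has been no virus circulating for over 4 or 5 months are highly likely to be false positives" in the diagnostic sense, "whether due to persistent antibody, cross-reactions, or other factors". Foreign travel is the only exclusion named. The section closes: "Data of this sort will be of great importance in defining the tails of the persistence distributions of IgM tests".

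Two other parts of the SAP bear on this:

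- **Section 5.4** says of IgM that "in some individuals it may persist for many months". It suggests treating a result as analytically true but diagnostically false "if IgM is due to an infection acquired many months before the pregnancy".
- **Sections 7.1 and 7.4** set the window for maternal infection at week -2 to delivery. Section 7.4 puts it this way: "Although the period of interest is between just before conception and delivery". Appendix 2 (A2.1) uses the same starting point, because its 1-Sp term multiplies the probability of no infection since week -2.

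**The concern.** The two descriptions of a diagnostic false positive do not match. In 5.4 the infection came well before the pregnancy. In 8.2.3 it is enough that no virus has circulated for 4 or 5 months, and that period can begin inside the same pregnancy. Take a woman infected at week 8, tested at week 36 and still IgM+. The lag is 28 weeks, longer than either cutoff. Sections 7.1 and 7.4 count her as infected in pregnancy, in the first trimester, yet 8.2.3 would read her result as a probable false positive.

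If such results are counted against specificity, 1-Sp is too large for the quantity that Appendix 2 needs, which is the positive rate in women not infected since week -2. Section 7.6 identifies false-positive IgM as the main threat to the vertical transmission rate, so a biased 1-Sp would matter if it were carried into that adjustment.

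**Working it through.** **The plan's own figure.** The 4 or 5 months is asserted, not derived. One month is 365.25/12/7 = 4.348 weeks, so the cutoffs are c = 17.4 and 21.7 weeks. That is 17.4/12 = 1.45 and 21.7/12 = 1.81 times the stated mean persistence.

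**When the cutoff falls inside the pregnancy.** For a test at week g, the virus-free period begins at g - c. It lies inside the window if g - c > -2, that is g > c - 2, which gives week 15.4 (4 months) or 19.7 (5 months). The SAP gives no test weeks for this analysis and only a preterm threshold ("Number (%) preterm <37 completed weeks"), so the test weeks below are assumed.

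| Test week | Onsets in pregnancy but older than 4 months | Older than 5 months | Whole window to test |
|---|---|---|---|
| 28 | -2 to 10.6 (12.6 wk) | -2 to 6.3 (8.3 wk) | 30 wk |
| 36 | -2 to 18.6 (20.6 wk) | -2 to 14.3 (16.3 wk) | 38 wk |
| 40 | -2 to 22.6 (24.6 wk) | -2 to 18.3 (20.3 wk) | 42 wk |

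**How many such women would still be IgM+.** The SAP gives a mean but no IgM distribution. I assume a Weibull with mean 12 weeks: S(d) = exp(-(d/λ)^k), λ = 12/Γ(1 + 1/k). For a test at week 36, with circulation ending exactly at the cutoff and onset uniform from week -2 to 36 - c, p is the average of S(36 - u) over those onsets.

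| Shape k | S at 4 / 5 months | p at 4 / 5 months |
|---|---|---|
| 1 | 23.5% / 16.3% | 0.112 / 0.089 |
| 2 | 19.2% / 7.6% | 0.040 / 0.017 |
| 3 | 11.4% / 1.4% | 0.012 / 0.001 |

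**Overstatement of 1-Sp.** Let r be the proportion infected. True positives are r·p and real false positives are (1 - r)(1 - Sp). The relative excess in the count read as false is r·p / [(1 - r)(1 - Sp)]. The values r = 10% and 1% and Sp = 95% are the illustrations in section 7.6; Sp = 99% is my assumption. Shapes 1 and 2, both cutoffs:

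- r = 10%, Sp = 95%: from 0.0017/0.045 = 4% to 0.0112/0.045 = 25%.
- r = 1%, Sp = 95%: from 0.00017/0.0495 = 0.3% to 0.00112/0.0495 = 2%.
- r = 10%, Sp = 99%: from 0.0017/0.009 = 19% to 0.0112/0.009, about 125% (p unrounded).

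At shape 3 and 5 months, with r = 10%, the excess is about 0.3% (Sp 95%) or 1.5% (Sp 99%).

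**Choice of denominator.** These ratios use uninfected women as the denominator. If all tested women are the denominator, and women who have cleared IgM can still test falsely positive, the excess is r·p·Sp/(1 - Sp). For the first case that is 0.1 × 0.017 × 0.95/0.05 = 3% to 0.1 × 0.112 × 0.95/0.05 = 21%. If cleared women are in the denominator but assumed never to test falsely positive, the dilution can cancel the bias: apparent specificity then runs from 0.944 to 0.953 against a true 0.95. Nothing in the SAP supports that last assumption.

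**The case against.** Several points on the other side stand.

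- **No counting rule is set.** Section 8.2.3 describes relating positivity to 12 months of surveillance, and the 4 or 5 months is a remark about likelihood. A reader might infer that every such result will be scored as false; the text does not say so. However, a 12-month look-back by itself does not tell the analyst to start at the woman's own week -2, so the interpretation remains open to the error.
- **The route to the vertical transmission rate is not fixed.** Section 8.2 calls these analyses supportive and has them compared with ZIKA-VID. Section 7.6 requires adjustment for the whole testing algorithm, and A2.3 leaves the calculation open. A reader might infer that the transmission rate, or first-trimester infections in particular, will be biased. The SAP does not say that this estimate enters Appendix 2 directly.
- **Women are tested repeatedly.** An early infection in a woman already enrolled may have shown up on earlier tests. That helps classify her, but 8.2.3 does not make earlier results a condition.
- **Dual use is not in itself a contradiction.** Because 5.4 separates analytic from diagnostic truth, a long response from before the pregnancy can inform the persistence tail and still be diagnostically false. What is missing is only a safeguard against entering one result twice as separate evidence.
- **Size.** A reader might place every infection 20 weeks before the test, where 11-19% would still be IgM+ (Weibull shape 2 to exponential). With 10% infected that gives 1.1-1.9% of tests, or 23-38% of a 5% false-positive rate. That single lag overstates the effect, since most eligible onsets are older. Nor do the SAP's mean and its mention of some individuals establish that such cases are common.

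**Conclusion.** The concern holds in a limited form. For tests after about week 15 or 20, the inference in 8.2.3 conflicts with the window in 7.1 and 7.4 and with the sense of 5.4, and it can misread true early-pregnancy infections as failures of specificity. Earlier tests are unaffected.

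The bias is negligible where few women were infected and the false-positive rate is 5%, moderate at 10% infected and 5%, and potentially large at 10% infected with a false-positive rate near 1%. These figures rest on a test at week 36, circulation ending exactly at the cutoff, uniform onset before it, and an assumed persistence shape. A longer virus-free period or a shorter tail reduces them. Any consequence for the vertical transmission rate is conditional on the estimate being used in Appendix 2.

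**What to change.** In 8.2.3, count an IgM+ towards diagnostic 1-Sp only if surveillance shows no circulation from that woman's week -2 up to the test, with travel excluded. The required period is gestational age at test plus 2 weeks: 30 weeks at week 28, 38 at week 36 and 42 at week 40. All are within the 12-month look-back already planned. Let other IgM+ results inform infection and persistence through the likelihood in 7.4 and 7.5. Add a sentence that no result is entered as independent evidence on both specificity and the persistence tail.

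The change is to SAP wording and uses surveillance dates and gestational ages that the plan already relies on. The cost is that fewer late-pregnancy tests contribute to the specificity estimate, so it will be less precise.

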#### 8.3 Computational methods

Basic analyses of population epidemiology outcomes can be carried out in standard software such as SAS or STATA.

Wherever adjustment is required for sensitivity, cross-reactivity or specificity, the analyses are best carried out in Bayesian framework, because adjusted estimates require information on sensitivity and

Author: [name] (UNIVBRIS)

29

specificity in the form of probability distributions. Although a frequentist framework can be used, by inverting the relationship in the equations in section 8.1.2, thereby making the true prevalence a function of the observed prevalence, it then becomes technically difficult to prevent the confidence intervals for true prevalence estimates from going outside the (0,1) bounds that probability parameters must fall in.

In addition, combining information from multiple tests (*Appendix 6*) with correct propagation of uncertainty is readily achieved in a Bayesian multi-parameter evidence synthesis framework [11], but would otherwise require special software if frequentist software was to be used. Bayesian analyses will be undertaken in WinBUGS 1.4.3 or OpenBUGS.

# 9. Clinical outcomes in arbovirus-infected women and the impact of pregnancy

This is mainly a descriptive study of the natural history of ZIKV, DENV and CHIKV acquired in pregnancy. There will also be regular testing and follow-up of a cohort of mothers who did not acquire infection in pregnancy, allowing a three-way comparative element to look at natural history in women acquiring infection during pregnancy and after pregnancy, alongside uninfected controls.

#### 9.1 Analyses to be carried out

9.1.1 Spectrum of initial symptoms and risk factors for symptomatic presentation. Table 6 represents a sample table shell for analyses of initial symptoms. This can be further examined by regression to see if there are risk factors for the occurrence / non-occurrence of specific symptoms

Table 7 sets out an analysis of risk factors for symptomatic versus asymptomatic presentation. Both univariate and multivariate analyses are envisaged but it is not yet possible to specify which factors should be controlled for in a multivariate setting.

#### 9.1.2 Loss to follow-up. See Table 8.

9.1.3 Natural history: risk factors for subsequent clinical outcomes. These analyses focus on the subsequent development of clinical sequelae, following the initial presentation. Because there are time-varying risk factors, including pregnancy and infection status, this is best analyzed as a synthetic case-control study, considering each clinical outcome in turn.

As an illustration, we consider persistent joint pain as an outcome. All cases of persistent join pain will be identified, along with the time since the initial symptom presentation. For each case as many controls will be identified, up to a maximum of 10 (this number may be revised subject to the distribution of risk factors). To qualify as a control, a woman must have been under observation longer

Author: [name] (UNIVBRIS)

30

than the matched case without ever having experienced persistent joint pain. Control women will also be matched for center and for age at recruitment to the study, if possible to the nearest one or two years.

Matched logistic regression will then be used identify the role of risk factors in the development of persistent joint pain, including: infection (ZIKV, DENV, CHIKV, or no infection), symptomatic presentation initially, pregnancy, previous infection, socio-economic status or educational status, and so on. Table 9 illustrates the form of the output from this analysis. It is too early to specify which variables should be used to control for in multivariate analyses, and some recoding of variables may be needed.

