### Table 8. Women's cohorts: Completeness of follow up

		Recruitment	1m	4m	9m	12m
	Number of women					
ZIKV	Contributing data					
	Number lost to Follow-					
	ир					
	Number of women					
DENV	Contributing data					
	Number lost to Follow-					
	ир					
	Number of women					
CHIKV	Contributing data					
	Number lost to Follow-					
	ир					
Not	Number of women					
infected	Contributing data					
	Number lost to Follow-					
	ир					

Author: [name] (UNIVBRIS)

41

[figure not shown]
Table 9. Women's follow-up study - Natural history subsequent to initial presentation. Risk factors for a single specified clinical outcome.

sted Adjusted (95% CI) Rel Risk (95% CI)		Control	Cases	Risk factor
·	•			Infection
				ZIKV
				CHIKV
				DENV
1.0 (ref)	1			No infection
			nset	Pregnant at symptom of
				Yes
1.0 (ref)	1			No
			come onset	Pregnant at clinical outc
				Yes
1.0 (ref)	1			No
				Initial symptoms
				Yes
1.0 (ref)	1			No
				Mother's Age
				<19
				20-24
				25-29
1.0 (ref)	1			30+
		x infection	 r to the inde	Previous infection, prior
				ZIKV
				CHIKV
				DENV
1.0 (ref)	1			No infection
ef)	1			CHIKV DENV

Author: [name] (UNIVBRIS)

42

Figure 1. Schematic influence diagram. Showing the relationships between data and parameters in an analysis of vertical transmission rate and risk of clinical outcomes of vertical transmission. Rectangles denote data and ellipses parameters. Subscript *i* denotes mother-child-specific items, (t) denotes dependency on gestational age. Mother-child data and parameters are outlined in red. Items outlined in green and green influence arrows apply only in analyses which include adjustment for sensitivity, specificity and cross-reactivity of persistence tests.

Author: [name] (UNIVBRIS)

43

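### Table 9 plans relative risks for Mother's Age although Section 9.1.3 matches controls to cases on age, which leaves the age row weakly informed and, for a gradual age effect, strongly attenuated

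*SAP*

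**What the plan says.** Section 9.1.3 of the SAP uses persistent joint pain to illustrate how each later clinical outcome in the women will be analysed. Each case gets controls "up to a maximum of 10", drawn from women observed for longer than the case without the outcome. Then: "Control women will also be matched for center and for age at recruitment to the study", with the tolerance "if possible to the nearest one or two years".

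On the model: "Matched logistic regression will then be used identify the role of risk factors in the development of persistent joint pain". Besides infection, the listed factors are "symptomatic presentation initially, pregnancy, previous infection, socio-economic status or educational status, and so on". Age is not named. The section adds that "Table 9 illustrates the form of the output from this analysis" and that "some recoding of variables may be needed".

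Table 9 has columns for cases, controls, and unadjusted and adjusted relative risks with 95% intervals (the headings are broken in the text as read). One of its rows is Mother's Age, with bands that read <19, 20-24, 25-29 and 30+, the last being the reference at 1.0. Center, the other demographic matching factor, has no row. Table 7, which is not a matched analysis, uses <20, 20-24, 25-29 and 30+.

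**The concern.** A matched logistic regression compares each case only with her own controls. A covariate contributes only where it differs within a set, and matching on age is meant to remove most such differences. The plan therefore takes out the information on age and then reserves a row to report it.

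The row would still fill with numbers. A value close to 1 with a wide interval could be read as evidence that age has little bearing on sequelae, when the design had largely fixed that result. The bands as read also leave age 19 without a category.

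**Working it through.** The SAP gives no case numbers, age distribution or expected age effect for this analysis, so there is no figure of its own to reproduce. All numerical inputs below except the 1- and 2-year tolerances and the bands are assumptions.

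**1. Which sets carry information.** The inner bands are five years wide. A set within 2 years of the case spans at most five consecutive ages, so it can touch at most two bands. No set can hold both a woman under 20 and one aged 30 or more, whose ages differ by at least 11 years. The contrast of <20 with 30+ must be chained across three cut-points, each informed only by women close to it. In a simulation of 300 cases with 4 controls each (ages 16-44 centred at 26), 38-45% of sets contained more than one band with a 2-year match, 21-24% with a 1-year match and none with exact matching.

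**2. Hand calculation for a smooth effect.** Assume a fourfold change in odds over 15 years, so the log odds ratio per year is ln(4)/15 = 1.386/15 = 0.0924.
- 1-year match: the only pair of ages straddling a cut-point is adjacent (such as 24 and 25), a difference of 1 year. Over three cut-points: exp(3 × 1 × 0.0924) = exp(0.277) = 1.32.
- 2-year match: the straddling pairs are 24/25, 23/25 and 24/26, with mean difference (1+2+2)/3 = 1.67 years if equally weighted. Over three cut-points: exp(3 × 1.67 × 0.0924) = exp(0.462) = 1.59.

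A fourfold contrast would thus print as about 1.6 or 1.3.

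**3. Simulation.** Odds ratio for <20 against 30+, with the standard error of the log odds ratio in brackets where available. The 4-control runs were simulated with risk rising with age and are inverted here (for example 1/0.23 = 4.3).

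| Assumed truth and set-up | No age match | Within 2 years | Within 1 year |
|---|---|---|---|
| Smooth; 600 cases, 5 controls | 3.9 | 1.6 | 1.3 |
| Smooth; about 300 cases, 5 controls | 4.1 (0.23) | 1.8 (0.57) | 1.3 (0.77) |
| Smooth; 300 cases, 4 controls | 4.3 (0.33) | 2.0 (0.84) | 1.4 (1.07) |
| Steps, true 3.0; about 300 cases, 5 controls | 3.4 (0.22) | 2.7 (0.56) | 2.3 (0.79) |
| Steps, true 4.0; 300 cases, 4 controls | 3.7 (0.32) | 2.8 (0.69) | 3.1 (1.03) |

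The runs of about 300 cases have few replicates (8 or 12), so the step rows are noisy. Larger runs with true steps of 3.0 gave matched estimates near 2.9 (600 cases, 5 controls) and, over 150 replicates with 600 cases and 10 controls, 2.9 within 2 years and 2.6 within 1 year.

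**4. Precision.** Standard-error ratios, matched to unmatched, from the table: 2-year match 0.57/0.23 = 2.5, 0.84/0.33 = 2.5, 0.56/0.22 = 2.5 and 0.69/0.32 = 2.2; 1-year match 0.77/0.23 = 3.3, 1.07/0.33 = 3.2, 0.79/0.22 = 3.6 and 1.03/0.32 = 3.2. The 600-case, 5-control run put the ratio at three to four.

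**5. If the unadjusted column ignores the sets.** With true step odds ratios of 0.25/0.50/0.75 for the three younger bands, crude values were 0.89/0.90/0.91 with a 2-year match, 0.95/0.96/0.97 with a 1-year match and about 1.0 with exact matching. The match alone pulls them to 1.

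**6. Bands.** Taken as read, 18 and under falls in <19, and 20 upwards is covered. Age 19 falls nowhere.

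**The case against.** Table 9 is a shell that illustrates a form of output. Section 9.1.3 says it is too early to fix the adjustment variables, allows recoding, and does not name age among its risk factors. An age row beside case and control counts is a sensible display of how well the match worked. Section 9 describes itself as mainly descriptive, Section 10.4 places these outcomes under hypothesis formation, and objective 2.3 does not name age as a cofactor. All of this stands and limits the weight of the point. It does not remove it: the row carries a reference category for relative risks, and no recoding restores information that the match has taken out.

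A reader might infer that the age effect cannot be estimated at all. The documents do not support that. The tolerance is one or two years and applies only where possible, so age remains weakly identified; only exact matching would make it inestimable.

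A reader might also infer that matching biases the age contrast whatever the truth. Replicated runs with risk stepping exactly at the cut-points stay near the true value; the loss there is precision.

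Finally, a reader might infer that 19-year-olds will be dropped from the model. The table is visibly damaged in the text as read, <19 may be a lost ≤19, and a shell label is not final coding.

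**Conclusion.** The inconsistency holds in limited form. Section 9.1.3 matches on age, and its output table plans relative risks for age. With a gradual age effect the printed contrast would be strongly attenuated, from about 3.9 to 1.6 (2-year match) or 1.3 (1-year match). With true steps it would be roughly unbiased but with a standard error about three times larger, two to four times across the runs.

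These sizes rest on an assumed age distribution, assumed case numbers and an assumed effect of about fourfold (smooth) or three- to fourfold (steps). The attenuation under a smooth effect and the loss of precision do not depend on the number of cases. Estimates for infection, pregnancy and the other risk factors are not harmed by the age match. Severity is minor: one row of a hypothesis-forming table. The age-19 gap is at most a label slip and may be a reading error.

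**What to change.** In Table 9, remove the relative-risk cells for Mother's Age and keep case and control counts by band, labelled as describing the match. Add a sentence to Section 9.1.3 that age at recruitment is controlled by matching and its effect is not estimated. If the age effect is itself wanted, age has to come out of the matching factors and enter as a covariate; in the simulations the model without age matching recovered it.

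If the age row is kept in any form, check the lowest band in the source file and align it with <20 in Table 7.

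The cost is one sentence and one table row, with no change to data collection.
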